## **13.2. Extent of Study Drugs Exposure**

Listings of exposure of study drugs (veledimex and Ad-RTS-hIL-12) will be provided by treatment arm, dose cohort and subject ID for the OSP.

### **13.2.1. Ad-RTS-hIL-12 Injections**

The total volume received, the number of sites and whether the dose was modified will be tabulated by subject ID.

### **13.2.2. Veledimex Exposure**

The number and percentage of subjects exposed to the veledimex study drug will be provided by treatment arm and the dose cohort, for the OSP.

Listings of treatment compliance and modification of study drug veledimex will be provided by the treatment arm, dose cohort, and subject ID for the OSP.

Veledimex study drug exposure will be summarized by subject ID for:

- Duration of exposure
  - In days, defined as last dose date – first dose date + 1
- Cumulative dose
  - Actual cumulative dose (mg), defined as the sum of all doses taken during the treatment period.
  - Expected cumulative dose (mg), defined as sum of all doses assigned during the treatment period.
- Dose intensity
  - Actual dose intensity (mg/day), defined as the actual cumulative dose (mg) divided by the duration of exposure (days).
  - Expected dose intensity (mg/day), defined as the expected cumulative dose (mg) divided by the duration of exposure (days).

- BSA-adjusted dosing
  - defined as the actual administered dose divided by body surface area (BSA).
  - BSA-adjusted dosing <75%, 75%-125%, and >125% will be categorized for summary.

### 13.3. Treatment Compliance and Modification

Veledimex study drug treatment compliance and any modifications to the dose and schedule of treatment will be summarized by subject ID for the following variables:

- Relative dose intensity (%)
  - defined as the actual dose intensity (mg/day) divided by the expected dose intensity (mg/day), expressed as a percentage.
- Dose interruptions by subject ID
  - The number of subjects with any dose interruptions
  - Time in days from first dose date to date of first dose interruptions for any reason:
  - Time in days from first dose date to date of first dose interruption due to AEs
  - Total days of dose interruptions due to AEs
- Dose reduction
  - Number of subjects who were classified as receiving a dose reduction
  - Time in days from first dose date to the date of first dose reduction due to AEs
  - Total days of dose reduction due to AEs for subjects experiencing a dose reduction

### 13.4. Clinical Laboratory Assessments

Clinical laboratory assessments include hematology, coagulation, serum chemistry and urinalysis. Laboratory tests will be performed in a central laboratory. Laboratory values will be converted to standardized units. Only numerical values will be used for summary of continuous parameters.

For hematology, coagulation and serum chemistry laboratory parameters, subject listings will be provided for values at baseline and changes from baseline instead of descriptive summary tables by treatment arm, dose cohort and visit for the OSP.

In addition, laboratory test results will be categorized by CTCAE toxicity grades according to the normal ranges of the central laboratory. Subject listings will provide the shift from baseline to worst post-baseline extreme values denoting the visit for which the worst post-baseline shift occurred. Laboratory results with toxicity grades missing at either baseline or at post-baseline will not be used for summarizing the worst post-baseline shift by subject ID. The number of subjects who have both baseline and post-baseline laboratory values will be summarized where applicable.

Urinalysis laboratory parameters are summarized by subject ID (instead of Frequency tables used to summarize the urinalysis laboratory parameters by treatment arm and dose cohort, and visit.).

Separate listings by subject ID for each subject ID visit will be summarized for all laboratory tests where applicable for the OSP. Both laboratory parameters' values in the original unit collected and standardized units will be listed.

### **13.5. Vital Signs including Weight**

The vital signs' parameters include systolic and diastolic blood pressure (mmHg), heart rate (bmp), respiratory rate (breaths/minute), temperature ( $^{\circ}\text{C}$ ) and weight.

Observed vital signs will be summarized in listings by subject ID for the OSP (instead of using descriptive statistics by treatment arm, dose cohort and visit for the OSP).

Conversion of temperature from Celsius to Fahrenheit is defined:

$$\text{Temperature } (^{\circ}\text{C}) = (\text{Temperature } (^{\circ}\text{F}) - 32) \times 5/9$$

Listings of vital signs, height and weight will be provided by subject ID for the OSP.

### **13.6. Physical Exams**

Physical exams including general physical exam and targeted neurological exam will be tabulated by subject ID for the OSP.

### **13.7. Electrocardiogram (ECG)**

Where applicable, a summary of actual values and changes from baseline will be provided by Subject ID for the OSP. This is in lieu of presenting the overall interpretation of ECG results be summarized using frequency tables by treatment arm, dose cohort, and visit for the OSP.

### **13.8. Lansky, Karnofsky and ECOG Performance Status**

Where applicable, a summary of actual values and changes from baseline will be provided by Subject ID for the OSP.

Scores and changes from baseline for Lansky, Karnofsky and ECOG Performance Status will be tabulated by subject ID for the OSP.

Listings will be presented by subject ID based on EP for Lansky, Karnofsky and ECOG Performance Status.

### **13.9. Pregnancy Test**

Pregnancy test results will be listed by arm and dose cohort, visits, and subject ID for the OSP.

## **14. EFFICACY ANALYSIS**

Tumor response will be assessed using iRANO criteria at Day 14, 4 weeks (Day 28  $\pm$  7 days), 8 weeks (Day 56  $\pm$  7 days), and every 8 weeks ( $\pm$  7 days) thereafter for all subjects. The analysis will be performed by arm and dose cohort for ESP.

Tumor assessments after the initiation of further anticancer therapy are excluded for the assessment of best overall response.

Listing will have presented for tumor response for OSP. Listing will be presented for all efficacy data by arm and dose cohort, and visit for ESP.

### **14.1. Tumor Response by iRANO**

Frequency tables will be used to summarize response of tumor assessment for target, non-target and non-enhancing lesions, and overall response by arm and dose cohort, and visit using ESP.

### **14.2. Objective Response Rate (ORR)**

ORR is the proportion of subjects meeting iRANO response criteria which is defined as sum of partial responses plus complete responses. ORR will be summarized using frequency tables by arm and dose cohort, and visit with 2-sided 95% exact binomial confidence interval (CI).

A figure similarly to a forest plot will be provided to display the response rates of each arm and dose cohort systematically along with a 2-sided 95% exact binomial confidence CI.

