[REDACTED] be of diagnostic quality. The brain is to be imaged using the same method(s) used throughout the study. Measurable target lesions should be selected and measured per iRANO criteria guidelines for adults, pending issuance of pediatric criteria. Repeat scans to confirm progression should be completed at 4 weeks and preferably again at 12 weeks (per iRANO) after first documentation of progression. Additional tumor response assessments, as well as a posttreatment diagnostic brain biopsy, may be performed at the discretion of the investigator as part of providing standard-of-care treatment in accordance with current iRANO guidelines.

^x The Day 28 (\pm 7 days) and Day 56 (\pm 7 days) MRI scans are required for all subjects, including those with unconfirmed disease progression, to ensure that more slowly declining tumor burden in response to therapy is noted. For 2 years, subjects without confirmed disease progression should continue to have tumor assessments performed every 8 weeks as per standard practice until disease progression has been identified (first documentation) and confirmed (12 weeks after first documentation). MRI scans and reports should be sent to the Sponsor per the Sponsor's defined process.

^y The MRI scan designated on Day 2 has an allowable window of \pm 24 hours and will be considered the baseline scan for tumor response assessments.

^z Additional tumor, blood, and CSF (if available) samples to be collected, if available, as part of standard-of-care procedures. For example, additional CSF samples may be obtained at the time of MRI scans whenever sedation is clinically indicated or if an Ommaya reservoir is implanted.

^{aa} The tumor sample on Day 0 should be collected prior to Ad-RTS-hIL-12 injection.

^{bb} A tumor sample should be collected if there is a concern of pseudo-progression. The biopsy at Day 56 is strongly recommended. Patients should remain on-study for continued follow-up until confirmed progression per iRANO or the patient meets other withdrawal criteria.

^{cc} Every 8 weeks from Day 56.

^{dd} The patient should be contacted every day during the treatment period to discuss clinical status and updates on current/new adverse events. If the patient is discharged prior to Day 14, follow-up may occur via telephone. Successful contact and contact attempts will be documented in EDC.

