16.4.3. Tumor Response and Overall Survival Analyses

Tumor response analysis will be performed on the ESP. The Investigator assessment of ORR and PFS will be determined for each cohort according to the baseline (Day 2 \pm 24 hours) assessment, with tumor response characterized by iRANO (Okada, Weller et al. 2015) criteria for adults, pending issuance of pediatric criteria. The OS is defined as the duration of time from the first dose of study drug to the date of death or, for subjects who are still alive two years after first dose of study drug, subjects will be censored at the last follow-up contact date. A 2-sided confidence interval will be computed for the ORR. The PFS and OS will be analyzed using Kaplan-Meier methods.

16.4.4. [REDACTED], PK, and [REDACTED]

Veledimex PK parameters will be determined based on blood (plasma) levels of veledimex using [REDACTED]

[REDACTED] here possible, descriptive statistics of the PK parameters will be provided; individual subject veledimex concentrations, actual sampling times, and PK parameters will be listed.
[REDACTED]

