## 7.1. General Statistical Procedure

The descriptive statistics for continuous variables (e.g., age) will be the number of subjects with a non-missing value of the variable (n), mean, standard deviation (SD), median, quartiles (Q1, Q3), minimum and maximum. Mean, median, Q1, and Q3 will be reported to 1 more decimal place than the raw data. The SD will be reported to 2 more decimal places than the raw data. Minimum and maximum will be reported the same as the original data.

In addition to the above descriptive statistics, coefficient of variation (CV%), geometric mean and geometric CV% will also be used to summarize the drug veledimex concentration where applicable.

Coefficient of variation CV% is calculated as  $100 \times (\text{SD}/\text{mean})$ . Geometric CV% is calculated as follows:  $\text{CV\%} = 100 \times \sqrt{\exp(\hat{\sigma}^2) - 1}$ , where  $\hat{\sigma}^2$  denotes the estimated variance of the log-transformed values.

Categorical variables will be summarized by frequency table which includes the number of subjects with a response in the category and the percentage of the total number of subjects in that particular column. Unless otherwise stated, missing responses will NOT be included in the analysis. Percentages will be rounded to one decimal place.

Unless otherwise stated, data will be tabulated by arm and dose cohort, and overall according to the defined population. If dose escalation is stopped before reaching higher veledimex doses, those columns will be omitted from the summaries.

All listings will be ordered by arm and dose cohort, and subject ID for available data.

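### SAP 14.2 tabulates ORR visit by visit and never ties the cohort rate to best overall response or to a stated denominator

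*SAP*

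**What the plan says.** **Definition and summary.** SAP 14.2 states: "ORR is the proportion of subjects meeting iRANO response criteria which is defined as sum of partial responses plus complete responses". It then says: "ORR will be summarized using frequency tables by arm and dose cohort, and visit with 2-sided 95% exact binomial confidence interval (CI"). The same section adds a forest-type figure to "display the response rates of each arm and dose cohort systematically along with a 2-sided 95% exact binomial confidence CI"; this has no visit dimension. SAP 4.6 gives the same CR-plus-PR definition and assigns ORR to each cohort. Neither section mentions best response, a reference visit, or how to count a subject without a scan. SAP 14 sets the population as the ESP.

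**Protocol.** Section 16.4.3 has ORR determined per cohort and says: "A 2-sided confidence interval will be computed for the ORR". Section 16.2 gives preliminary assessment of response as one reason for the size of the expansion.

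**Missing responses.** SAP 7.1 bases percentages in frequency tables on all subjects in the column. The next sentence reads: "Unless otherwise stated, missing responses will NOT be included in the analysis". SAP 14.2 makes no exception.

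**Scans after other treatment.** SAP 14 says: "Tumor assessments after the initiation of further anticancer therapy are excluded for the assessment of best overall response". Protocol 13.1 ends response assessments at the first of confirmed progression, start of other therapy, or two years after the injection. Footnote x of the protocol's schedule table says "subjects without confirmed disease progression should continue to have tumor assessments performed every 8 weeks" and does not mention new therapy.

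**Scope.** The protocol synopsis plans subject listings of ORR and PFS if there is no expansion. SAP 6.1 likewise avoids statistical summaries of very small samples.

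**The concern.** An objective response rate is normally one number per cohort: the share of treated, analysable subjects who ever reach CR or PR within the assessment window. A table of response status at each visit answers a different question, namely who is in response among those counted on that day.

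In DIPG the difference is not academic. Many subjects will have died or reached confirmed progression well before two years, and both end scanning. If subjects without a scan leave the denominator, those who remain are selected for doing well. With an exact interval at every visit and no visit named as the estimate, a favourable visit could be quoted after the data are seen. The result would not be comparable with ORR in other studies. It would also bear on the response assessment that protocol 16.2 uses in sizing the expansion.

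**Working it through.** Neither document states a target ORR, a null rate or a precision, so there is no planned figure to reproduce. What follows is an illustration of what the text permits.

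**Inputs**
- N = 30: maximum expansion, protocol 16.2.
- One-year survival in DIPG below 45%: background, protocol 5.1 and SAP 1. The bound of 45% is used as an assumption, with exponential decline.
- Scans every 8 weeks from Day 56: protocol schedule table.
- Assumed: 3 responders whose responses last; all deaths among non-responders; every survivor scanned.

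**Formulas**
- Subjects left at week t: n(t) = 30 × 0.45^(t/52).
- Rate: r/n.
- Exact (Clopper-Pearson) 95% limits: lower = Beta quantile 0.025 with parameters (r, n − r + 1); upper = Beta quantile 0.975 with parameters (r + 1, n − r).

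**Reading A: missing responses dropped**

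| Time | Subjects left | Rate | 95% exact CI |
|---|---|---|---|
| Start | 30 | 3/30 = 10.0% | 2.1 to 26.5 |
| Day 280 (week 40) | 16.2, taken as 16 | 3/16 = 18.8% | 4.0 to 45.6 |
| Day 336 (week 48) | 14.4, taken as 14 | 3/14 = 21.4% | 4.7 to 50.8 |
| Day 392 (week 56) | 12.7, taken as 13 | 3/13 = 23.1% | 5.0 to 53.8 |

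At exactly one year, 30 × 0.45 = 13.5. One year is not a scheduled visit; Days 336 and 392 lie on either side of it.

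Sensitivity:
- One lasting responder: 1/30 = 3.3% becomes 1/13 = 7.7%. Two: 2/30 = 6.7% becomes 2/13 = 15.4%.
- Lower survival (exponential through the other background bound, 10% at two years): 10.4 subjects remain at week 48, so 3/10 = 30.0%.
- Equal attrition in responders and non-responders: 3 × 0.45 = 1.35 and 1.35/13.5 = 10.0%. There is no inflation.
- Only deaths are removed here. Stopping scans at confirmed progression would shrink the denominator further.

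**Reading B: column total as denominator**
- Three lasting responses give 3/30 = 10.0% at every visit, so nothing inflates.
- Three subjects each in response at one different visit give 1/30 = 3.3% (0.1 to 17.2) at each of those visits, although 3/30 = 10.0% responded.
- Six subjects who ever respond, with at most three in response at any one visit, give a maximum of 3/30 = 10.0% (2.1 to 26.5), against 6/30 = 20.0% (7.7 to 38.6).

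Neither reading makes the by-visit table an ORR in general. Reading A can overstate it and Reading B can understate it.

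**The per-cohort figure.** It has the right shape, with one rate and one interval, but SAP 14.2 does not say which rate feeds it. Under the illustration above, a programmer could defensibly plot 10.0%, 21.4% or 23.1%.

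**Scans after new therapy.** Protocol 13.1 stops response assessments at other therapy, and SAP 14 drops later scans from best overall response. SAP 14.1 and 14.2 tabulate response by visit and do not refer to best overall response, so the SAP exclusion does not expressly reach those tables. Later anticancer therapy is foreseen, since protocol 11 records it for two years.

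**The case against.** The strongest reply is that the pieces of a proper ORR are already present. The figure in 14.2 gives one rate and interval per cohort. The exclusion rule in SAP 14 presupposes that a best overall response is derived. Protocol 13.1 already ends assessments at other therapy. The column-total sentence in SAP 7.1 supports a fixed denominator. On this view an experienced programmer would produce the conventional ORR anyway.

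Much of this stands, and it limits the point:
- A reader might infer that the SAP produces no single ORR. It does plan one rate per cohort; what is missing is its definition.
- A reader might infer that scans after new therapy count as response. Protocol 13.1 and SAP 14 point the other way. The remaining gap is only that the by-visit tables are not expressly covered if such scans exist.
- A reader might take it as settled that unscanned subjects leave the denominator. SAP 7.1 supports either reading.
- A reader might infer that the rate must rise. It rises only if missing responses are dropped and responders outlast non-responders; with equal attrition it stays at 10%.

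The reply does not supply the missing definition. Convention is not a pre-specified rule, and the only ORR table described carries an interval at each visit.

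**Conclusion.** The point holds as a gap in definition with a real numerical consequence. SAP 14.2 does not link ORR to best overall response, does not fix its denominator, and places exact intervals on visit-specific rates that are not the per-cohort ORR of protocol 16.4.3.

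The illustrated inflation, from 10.0% to 23.1% at about one year with no new response, rests on four assumptions: missing responses are dropped, the 3 responses last, one-year survival is 45%, and all deaths fall among non-responders. The survival figure is a background bound, not a prediction for this trial. Under the column-total reading the error runs the other way, because responses at different visits are never added together.

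The point applies mainly if the Safety Review Committee opens the Phase II expansion, since listings replace estimates otherwise. It should be corrected before database lock. It does not affect the primary safety endpoint.

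**What to change.** In SAP 14.2:
1. Define ORR as the proportion of all ESP subjects in the cohort whose best overall iRANO response is CR or PR.
2. Use post-baseline scans up to the earliest of confirmed progression per iRANO, new anticancer therapy, or two years, matching protocol 13.1. The cut-off must be confirmed progression. The protocol requires the Day 28 and Day 56 scans after unconfirmed progression and keeps subjects on study because of pseudo-progression; an earlier cut-off would discard responses it means to capture.
3. Count subjects with no evaluable post-baseline scan as non-responders, and state that this overrides the general rule in SAP 7.1.
4. Give one exact 95% interval per cohort and use this rate in the forest-type figure.
5. Keep by-visit response as descriptive output without intervals, and apply the new-therapy exclusion to every response table.

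The cost is a paragraph of SAP text and one table shell. No new data or visits are needed. The reported ORR may be slightly less favourable, because unevaluable subjects stay in the denominator.

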### **14.3. Progression Free Survival (PFS)**

Progression-Free Survival (PFS) will be calculated as the time from baseline (Day 2) to date of disease progression or death, whichever occurs first. A subject who has neither progressed nor die will be censored on the date of last tumor response assessment. Subjects without valid baseline will not use for analysis. Subjects without post-baseline disease progression assessment will be censored at date of last non-progression disease response assessment or withdrawal.

The Kaplan-Meier (KM) method will be used to estimate the distribution of PFS for each arm and dose cohorts. Survival time will be summarized using descriptive statistics including 95% exact CI for median survival. Progression free survival rate at end of visit will also be included with 95% exact CI.

KM plots of PFS will be provided to graphically present the survival risk for each arm and dose cohort.

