#### **4.6. Efficacy Evaluations**

The secondary efficacy endpoints include Investigator assessment of ORR, PFS and OS. The Investigator assessment of ORR and PFS will be determined for each cohort according to the baseline (Day 2) iRANO assessment, with tumor response characterized by iRANO criteria for adults, pending issuance of pediatric criteria.

The following variables will be used for the determination of tumor response variables and OS by subject ID:

[figure not shown]
- Tumor response by iRANO for
  - Target, non-target and non-enhancing lesions.

- Overall response
- ORR defined as sum of partial responses and complete responses.
- PFS defined as duration of time from first dose of the study drug to the date of disease progression, or death of any causes, whichever occurs earlier, plus 1 day.
- OS defined as the duration of time from first dose of the study drug to the date of death. Subjects who are still alive 2 years after first doses of study drug will be censored at the last follow up contact date.

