### **14.4. Overall Survival (OS)**

OS is defined as the duration of time from first dose of the study drug to the date of death. Subjects who are still alive 2 years after first does of study drug will be censored at the last follow up contact date.

Details of death and survival time will be listed.

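### SAP 4.6 and SAP 14.3 define PFS with different start days and day counts, and two rules in 14.3 exclude or censor subjects with no exception for those who died

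*SAP*

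**What the plan says.** SAP 4.6 (Efficacy Evaluations): "PFS defined as duration of time from first dose of the study drug to the date of disease progression, or death of any causes". It takes the first of these two dates and then adds one day to the duration.

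SAP 14.3 (Progression Free Survival) makes four statements in sequence:

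- Definition: "Progression-Free Survival (PFS) will be calculated as the time from baseline (Day 2) to date of disease progression or death, whichever occurs first".
- General censoring: "A subject who has neither progressed nor die will be censored on the date of last tumor response assessment".
- Exclusion: "Subjects without valid baseline will not use for analysis".
- No post-baseline scan: "Subjects without post-baseline disease progression assessment will be censored at date of last non-progression disease response assessment or withdrawal".

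SAP 14.4 (Overall Survival): "OS is defined as the duration of time from first dose of the study drug to the date of death". No day is added, and SAP 4.6 adds none to OS either.

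Protocol 16.4.3 says "The PFS and OS will be analyzed using Kaplan-Meier methods" and defines the OS start, but states no start date for PFS. It does say that ORR and PFS are determined according to the baseline assessment at Day 2 ± 24 hours.

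The baseline scan window also differs. SAP 7.1.1 and footnote y of SAP Appendix 1 allow any time within 72 hours of injection. Protocol Table 1, footnote y, allows Day 2 ± 24 hours.

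**The concern.** Two programmers who each follow the SAP could produce different PFS times for every subject. For some early deaths they could also disagree on whether there was an event at all. SAP 7 treats its analyses as a priori because they are defined before database lock; choosing between two written definitions after lock would not meet that standard.

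The start-day difference is a near-constant shift of a few days. The handling of deaths matters more. The general censoring sentence in 14.3 is limited to subjects who neither progressed nor died, but the two sentences after it carry no such limit. A subject who dies before the first post-baseline assessment at Day 14 is an event under the opening sentence of 14.3 and censored under its last rule. A subject who dies without a valid baseline scan is an event under 4.6 and absent from the analysis under 14.3.

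**Working it through.** The documents give no PFS sample size, event count or power, so there is no planned figure to reproduce.

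**1. Start day and day count**

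Inputs: the day of injection is Day 0 (SAP 7.1.1). First dose of study drug falls on Day 0 in both arms: the pre-resection veledimex dose in Arm 1 and the injection in Arm 2 (Protocol Table 1, footnote h, and Protocol 10.2). Let the event fall on Day d and the baseline scan on Day s.

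- SAP 4.6: PFS = d - 0 + 1 = d + 1.
- SAP 14.3: PFS = d - s.
- Gap = (d + 1) - (d - s) = 1 + s.

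At nominal Day 2 the gap is 3 days: 2 from the start date and 1 from the added day. An event on Day 56 is 57 days under 4.6 and 54 under 14.3. If the actual scan date is used:

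| Scan window | s | Gap (days) |
|---|---|---|
| Protocol, Day 2 ± 24 hours | 1 to 3 | 2 to 4 |
| SAP, within 72 hours | 0 to 3 | 1 to 4 |

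If 14.3 is meant to add a day without saying so, the gap is s: 2 days at Day 2, 1 to 3 in the protocol window and 0 to 3 in the SAP window.

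For a death on Day d without progression, PFS under 4.6 is d + 1 and OS is d. PFS then exceeds OS by 1 day, which should not be possible.

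**2. One early death traced through the rules**

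Take a death on Day 10, with a Day 2 baseline scan and none later.

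- SAP 4.6: event at 10 + 1 = 11 days.
- SAP 14.3, first sentence: event at 10 - 2 = 8 days.
- SAP 14.3, last rule: censored. If the baseline scan is the last non-progression assessment, the censoring time is 0.

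**3. Effect on Kaplan-Meier PFS when the lost deaths come first**

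Assume N subjects, of whom k die before Day 14, with no other event or censoring before those deaths. Let R(t) be the PFS curve of the other N - k subjects.

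- Deaths counted: S(t) = ((N - k)/N) × R(t).
- Deaths dropped, or censored before the first remaining event: S(t) = R(t).
- Ratio = N/(N - k).

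It makes no difference whether the k subjects are dropped, censored at baseline or censored at the date of death or withdrawal. In each case they leave the risk set before the first counted event.

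| | k = 1 | k = 2 | k = 3 |
|---|---|---|---|
| N = 30 | 30/29 = 1.034 | 30/28 = 1.071 | 30/27 = 1.111 |
| N = 35 | 35/34 = 1.029 | 35/33 = 1.061 | 35/32 = 1.094 |

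N = 30 is the protocol's maximum expansion and 35 is the SAP's upper figure. The values of k are assumptions.

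For a reading at 6 months, assume exponential PFS with median m months in the other subjects, so R(6) = 0.5^(6/m). The difference is (k/N) × R(6). With N = 30:

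- m = 5: R(6) = 43.5%; difference 1.5 points for k = 1 and 4.4 for k = 3.
- m = 3: R(6) = 25.0%; 0.8 and 2.5 points.
- m = 8: R(6) = 59.5%; 2.0 and 5.9 points.

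**4. The direction for a late death**

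Take N = 30 and m = 5, with one subject who has no valid baseline, or no post-baseline scan, and dies at month 12.

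- Death lost: S(6) = 43.5%.
- Death counted at month 12: S(6) = (29 × 0.4353 + 1)/30 = 45.4%.

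Here the literal rule lowers 6-month PFS by 1.9 points.

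**The case against.** The strongest reply is that the effects are small and the intent is plain. A 3-day shift is less than the ±7-day windows at Days 28 and 56 and far below the 8-week scan interval. The general censoring sentence shows that the author had death in mind. PFS is secondary and untested. Without the expansion, the protocol summary plans listings only, and SAP 6.1 avoids statistical summaries of very small samples. All of this stands, and it limits the weight of the point. It does not remove the conflict: listed PFS times also depend on the definition, and 14.3 itself asks for Kaplan-Meier estimates by arm and dose cohort.

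It can also be said that Protocol 16.4.3 ties PFS to the Day 2 assessment, which would support 14.3. That wording may mean only the reference scan for judging progression, since it covers ORR in the same sentence. It does not settle the start date either way, so a reader should not infer that the protocol requires first dose.

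Three stronger readings are tempting and are not supported:

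- A reader might infer that the exclusion and censoring rules always inflate PFS. Step 4 shows otherwise: the upward direction holds for deaths before the time point being read.
- A reader might infer from the by-visit tables in SAP 14.2 that ORR has no denominator. SAP 14 names the ESP, and SAP 7.1 gives a general rule for percentages and missing responses.
- A reader might infer a further shift of weeks because 14.3 does not say whether progression is dated at first documentation or at confirmation. The iRANO paper in Protocol Appendix 6, whose text is not available here, may settle this. Protocol 13.1 also limits the repeat scans to progression within 6 months of starting therapy.

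**Conclusion.** The point holds for the two PFS definitions and for the missing exception for death. No text in either document reconciles SAP 4.6 with SAP 14.3.

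The definitions differ by 3 days at nominal Day 2, by 2 to 4 days across the protocol scan window and by 1 to 4 across the SAP window. This takes 14.3 as written, with no added day. Under 4.6, PFS exceeds OS by 1 day for a death without progression.

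The loss of deaths depends on reading two sentences of 14.3 literally. The likely intent is that death governs, but the text does not say so. If k deaths precede both the time point and all other events, the inflation factor is 1.034 to 1.111 for N = 30 and k = 1 to 3. The number affected is unknown. It is probably small, because the first post-baseline assessment is at Day 14, and with k = 0 this part has no effect. The 6-month figures also rest on an assumed median.

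This should be fixed before database lock, but at modest priority: the endpoint is secondary, no test is stated, and the consequence is mainly for a Phase II expansion.

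**What to change.** - Use one PFS definition in SAP 4.6 and 14.3, with one start date. First dose of study drug would match OS; the essential requirement is that both sections agree.
- Use the same day-count convention for PFS and OS: add 1 day to both or to neither.
- Limit the last censoring sentence of 14.3 to subjects with no documented progression or death.
- State that a death is a PFS event even with no post-baseline scan, and that it is not lost through the exclusion for no valid baseline.
- Align the SAP baseline MRI window (SAP 7.1.1 and Appendix 1, footnote y) with the protocol's Day 2 ± 24 hours.

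No particular rule is proposed here for survivors without a valid baseline scan. Counting the deaths while giving survivors no follow-up would be open to question in its own right, so the sponsor should choose and state the handling.

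The cost is SAP wording and programming only. No new data, visits or subjects are needed.
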